5.4 WP4 – Identifying resource requirements (months 16-23)

This WP will characterise and quantify the resources involved in developing and sustaining AFCCs (Obj. 4) and address our third research question: What are the resource requirements for effective and sustainable AFCC interventions?

Design: We will work within the proposed SROI framework to describe the incremental resource use and costs associated with the 2-3 age-friendly projects per site selected in WP2 from the priority areas of work. The local ToCs developed in WP2 will guide our collection of data on 'inputs', or investments by stakeholders (Stage 1). We will follow established procedures for costing health and social care interventions (45, 46) using a combination of bottom-up and top-down approaches. This typically involves describing the elements of the interventions in order to identify material inputs to production (including in-kind and non-monetised resources e.g. free or peppercorn rent for venues, volunteer time), establishing relevant units for each project (per person, per session, per episode, etc.), collecting financial data and calculating the costs of each intervention.

Costing: Unit costs (e.g. for weighting inputs to the production of the interventions) will be drawn from nationally representative sources such as the PSSRU Unit Costs (47), the NHS Reference Costs (48) and other published sources and some locally relevant valuations (such as local market rents and public transport fare prices). Annual equivalent costs of capital assets (office equipment, furniture, assistive equipment etc.) will be calculated where necessary. Costs of non-monetised resources such as volunteer time and participants' time will be valued at the opportunity cost (relevant opportunity costs to be determined, but time could for instance be valued at national minimum wage or at national average wage).

Input costs data collection: Initial descriptive data on initiatives/projects will be collected via interviews with project leads and in-depth information sought through the use of a proforma (covering expenditure, budget and activity data) and telephone and written correspondence as required with project managers/staff. Depending on the stakeholders identified, other data collection, such as questionnaires for older people participating in the initiatives, may take place.

Analysis: The work will include sensitivity analyses to investigate the impact on results of varying key assumptions underpinning the costing exercise. For instance, we may consider the impacts of important variations between sites/project such as geographical variations in labour costs, scope and scale of projects and capacity, and alternative valuations of non-monetised resources.

The choice of stakeholders, inputs and valuation sources will be tabulated and issues arising in making these choices will be discussed in order to present the calculation of the SROI ratio as transparently as possible.

5.5 WP5 – Assessing SROI of specific interventions (months 22-28)

The SROI ratio is calculated by dividing the overall value of the outcomes by the cost of the AFCC intervention [(positive benefits – negative benefits)/costs] to represent the value created. The value of the benefits will be derived from WTP in WP3 and the costs of interventions will be derived in WP4. Although the idea of 'cashable and non-cashable' value is not in the spirit of SROI, direct monetary benefits (where available) will be described in a fully disaggregated way alongside accrued social value for relevant outcomes. Alternative financial proxies will be examined through sensitivity analysis.

In order to evidence outcomes, we will draw on existing data sources identified in the study sites, external reports and government statistics (WP2). We expect to have quantitative data for some of the outcomes, but in their absence, we will collect additional data using interviews and tailored nominal group consensus exercises with local stakeholders and members of the public to determine the quantity of outcomes accrued using subjective assessment. Short of being able to implement a randomised/quasi-experimental design, a predominantly qualitative approach will serve to identify, for each outcome, the proportion of observed change accounting for factors such as attribution, deadweight, displacement, drop-off/attrition to minimize the risk of over claiming benefits. Attribution is the proportion of the observed change that is due to taking part in or accessing the AFCC intervention. Deadweight is the proportion of change that people would experience over time, regardless of taking part in the intervention. Displacement is the proportion of change that is being displaced, for example, the council cancelling or rearranging other activities to make way for an arts group for older adults. In SROI, drop-off/attrition refers to the proportion of effects that drop off after the first year, rather than being the attrition rate of people taking part in the intervention (49). The SROI process explicitly addresses the duration of expected benefits of initiatives with stakeholders. To adjust for time preference, we will adopt NICE's latest guidance for conducting public health economic evaluations by an annual discount rate of 1.5% on both costs and health effects (sensitivity analyses will include discount rates used by other parts of NICE, and the HM Treasury Green Book 3.5% discount rate). Further sensitivity checks will include the observed/estimated change for the outcomes, financial proxies used, estimates of deadweight and attribution, value of inputs for production.

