5.1 Project plan outline

This 30-month project uses a mixed-methods design and comprises six complementary work packages (WP) that are aligned with the main steps of SROI evaluations (11): a succinct evidence synthesis (WP1); primary qualitative and quantitative data collection on intervention outcomes, costs, and social value (WP2-4); estimation of SROI (WP5); and consultation on practice use of study outputs, and on the blueprint of an online social value bank (WP6). As the study comprises complementary WPs, methods, analyses and study population vary between WPs therefore these are described specific to each WP, where appropriate.

The population in focus, i.e. target population of AFCC interventions, is current and future older adults living in urban, rural and coastal areas in England. 'Stakeholders' indicate policy and practice professionals, volunteers, and wider community, affected by AFCC. Selection of stakeholders and members of the public is critically important for equity reasons, given the weight of their value judgement in the SROI analysis.

For qualitative components we will work with key contacts and use purposive sampling and snowballing to recruit representative samples. For quantitative components we will recruit a representative panel of older adults with support from a specialised survey agency, combined with working with key contacts in our case study sites. The outcomes of interest are individual and community level health related outcomes (see ToC). The intervention will be the AFCC initiatives in the case study sites (n=4) with a specific focus on local priority areas of age-friendly work (e.g. housing, transport, arts & leisure; see WP 2 below), out of which 2-3 highly specific age-friendly projects (e.g. an age-friendly housing development) will be chosen from across the 4 sites (see WPs 4 & 5 below).

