Communities (ACRE)); health and social care sector (e.g. community nurses; carers); experts in social value (e.g. HACT); researchers in ageing.

Identifying interventions: The interventions will be the AFCC initiatives in the case study sites (n=4), with a specific focus on respective local priority areas of age-friendly work (e.g. housing, transport, arts & leisure) and consideration of inequalities. Consulting with stakeholders and members of the public across the research sites, we will select a total of 2-3 highly specific age-friendly projects per site within the priority areas of work (e.g. an age-friendly housing development) for later assessment (see WPs 4 & 5).

With input from the local stakeholders, we will identify existing data sources for the priority health-related outcomes and we will seek stakeholders' advice on additional data to be collected, and how we can best do this in efficient yet robust, locally appropriate and inclusive ways. Consultations to evidence outcomes (in particular for outcomes for which there is no routine monitoring) will take place later in the project (WP5) to give the research team time to analyse and integrate findings from WP1 and WP2 - a necessary step before evidencing outcomes.

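### Where quantitative data are lacking, the benefit side of the SROI ratio rests on late subjective judgement by groups that may include people who fund, lead or deliver the project, with no rule or analysis that separates them

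*Protocol*

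**What the plan says.** Section 5.5 (WP5) defines the SROI ratio as the net value of outcomes divided by the cost of the intervention. To measure outcomes it turns first to existing local data, external reports and government statistics. The fallback has two parts. One is individual: "We expect to have quantitative data for some of the outcomes, but in their absence, we will collect additional data using interviews". The other is group work, described as "tailored nominal group consensus exercises with local stakeholders and members of the public to determine the quantity of outcomes accrued using subjective assessment".

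On how much of the change to credit to a project, the same section accepts that no controlled comparison will be made ("Short of being able to implement a randomised/quasi-experimental design"). In its place, it says, "a predominantly qualitative approach will serve to identify, for each outcome, the proportion of observed change accounting for factors such as attribution". The other factors are deadweight, displacement and drop-off. The stated purpose is to limit over-claiming. Sensitivity checks will cover the estimated change, the financial proxies, deadweight, attribution and the value of inputs.

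On timing, Section 5.3 (WP2, months 1-12) says that consultations to evidence outcomes, above all those not routinely monitored, "will take place later in the project (WP5) to give the research team time to analyse and integrate findings". WP5 runs in months 22-28.

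On who is involved:
- Section 5.1 defines stakeholders to "indicate policy and practice professionals, volunteers, and wider community, affected by AFCC".
- Section 5.3 says that, in consultation with stakeholders and the public, "we will select a total of 2-3 highly specific age-friendly projects per site".
- Section 5.4 (WP4, months 16-23) treats project inputs as what stakeholders invest. It adds that further data collection, such as "questionnaires for older people participating in the initiatives, may take place".

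**The concern.** Where no data exist, the quantity of benefit is a judged figure. Nothing in the protocol prevents a person who funds, leads or delivers a project from being among those who judge it. A nominal group also ends in one agreed figure, so any difference between people with a stake in the project and residents without one may be lost unless individual scores are kept by role.

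The judgement is made late and no earlier reading is described, so for these outcomes change would have to be reconstructed rather than measured from a starting point. No comparison group is available to correct it. The deductions meant to guard against over-claiming come from a process that is itself mainly qualitative.

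At stake is a main deliverable: the SROI evaluations in the four case study sites (Section 4.4). A reader will look first at whether a ratio lies above or below 1, and moderate optimism in two or three multiplied inputs can move it across that line.

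**Working it through.** **No figure to reproduce.** WP5 states no ratio, sample size or expected range. The check is therefore a reading of the text, followed by an illustration on assumed values.

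**Reading the sections together**
1. Quantity (Section 5.5): consensus groups and interviews, stakeholders and public together, only where data are missing. The number of outcomes affected is not given.
2. Credited share (Section 5.5): mainly qualitative; the raters are not named.
3. Overlap of roles (Sections 5.1, 5.3 and 5.4 WP4): the stakeholder category covers people consulted on project selection and people who invest in projects. No section bars them from judging effects.
4. Timing (Sections 5.3 and 5.5): months 22-28. No baseline or repeat measure is described for these outcomes.
5. Checks (Section 5.5): inputs are varied. No ranges, no joint variation and no comparison by type of rater are stated.

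**How errors combine.** Following the structure in Section 5.5, for a single outcome:

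ratio ∝ quantity × attribution × (1 − deadweight) × (1 − displacement) / cost

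All error sizes below are assumptions.

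*Two inputs.* Quantity 10% too high; deadweight set at 40% when 50% is right:
- quantity alone: 1.10
- deadweight alone: (1 − 0.40)/(1 − 0.50) = 0.60/0.50 = 1.20
- together: 1.10 × 1.20 = 1.32

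With a factor of 1.32, any true ratio between 1/1.32 = 0.76 and 1 would be reported above 1.

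*Three inputs.* Assume true attribution of 50%, deadweight of 30% and displacement of 10% (attribution's base value and displacement cancel). Apply the same relative error to all three: quantity and attribution too high, deadweight too low.

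| Relative error | Calculation | Factor |
|---|---|---|
| +10% | 1.10 × 1.10 × (1 − 0.27)/(1 − 0.30) | 1.26 |
| +20% | 1.20 × 1.20 × (1 − 0.24)/(1 − 0.30) | 1.56 |
| +30% | 1.30 × 1.30 × (1 − 0.21)/(1 − 0.30) | 1.91 |
| −10% | 0.90 × 0.90 × (1 − 0.33)/(1 − 0.30) | 0.78 |
| −20% | 0.80 × 0.80 × (1 − 0.36)/(1 − 0.30) | 0.59 |

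If quantity alone is wrong, the factors are simply 1.10, 1.20 and 1.30. The arithmetic runs in both directions, and varying one input at a time understates the joint effect.

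**The case against.** The strongest reply is that the protocol knows about this problem. Section 1 lists the counterfactual as a weakness of SROI and promises disaggregated results from several perspectives. Section 5.4 (WP4) will tabulate and discuss the choice of stakeholders. Sections 5.1 and 6.2.2 call stakeholder selection critical because their judgement carries weight. Section 5.5 applies deductions and varies change, deadweight and attribution. Judgement is only a fallback, members of the public take part, and interviews are used too. Stakeholder involvement is also what defines SROI.

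Much of this stands, and it rules out several stronger readings that a reader might infer:
- **That the ratio is biased upward.** The protocol supports a risk only. Raters could also be too cautious.
- **That the consensus groups also set the deductions.** Section 5.5 gives them the quantity of outcomes and names nobody for the deductions.
- **That the raters are the people who ran or chose the project.** They may include such people. The research team makes the selection after consultation, and nothing says that the project leads who supply cost data will sit in the groups.
- **That the sensitivity checks are of no use.** They show how far the ratio moves when an input changes. They do not show whether interested raters gave different inputs from the rest.
- **That residents' scores should be the base case.** This would replace the method's stakeholder basis, and participating residents may favour their own project.

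What the reply does not supply is any separation of interested raters from others. Tabulating stakeholders in the costing work and selecting them with equity in mind are not rules on independence. Nor can this be left to an analysis plan that is not shown: the protocol itself fixes who is asked, how and when, and individual scores by role cannot be recovered after a group has agreed a single figure.

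**Conclusion.** The concern holds as a risk. For outcomes without data, the benefit side of the ratio depends on late, subjective judgement by groups that may include interested parties, with no stated baseline, independence rule or comparison by rater. The share credited to the project rests on a mainly qualitative process with unnamed raters. The result may be an overstated SROI ratio.

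The size is unknown. The factor of 1.32, and the range of 1.26 to 1.91 for errors of 10% to 30% in three inputs, assume that the errors all point the same way and that the outcome concerned drives the ratio. If judged outcomes make up only part of the benefit, the effect on the overall ratio is smaller in proportion. The point deserves a change before WP5 begins, because the remedy depends on how the scores are collected.

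**What to change.** Amend Section 5.5 as follows:

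1. Before any group discussion, obtain private individual scores for quantity, attribution, deadweight and displacement. Record each rater's role: funds, leads or delivers the project; takes part in it; other resident.
2. Hold the scoring before project costs or provisional ratios are shown to raters.
3. Calculate and report each SROI ratio with and without the raters who fund, lead or deliver that project. Vary quantity, attribution and deadweight jointly as well as one at a time.

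The consensus exercise can stay as planned; the private scores come before it and do not replace it. The cost is a short score sheet and a little more analysis. The main limitation is that the two village sites may have few raters without a link to the project, so the ratio without interested raters may rest on few scores there. The number of raters in each role should be shown beside each ratio.

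If the WP4 participant questionnaires go ahead, the shortlisted outcome items could be added. This is optional: the questionnaires are not certain, WP4 (months 16-23) overlaps WP5 (months 22-28), and for projects already running the reading would not be a true baseline.

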5.6 WP6 – Practitioner consultation (months 27-30)

The final work package is dedicated to engagement and consultation with national practice-based stakeholders from communities with an age-friendly agenda beyond the research sites. This will take place through an end-of-project event, and it will be supplemented by presentations/workshops at national or regional practitioner-focused events, such as the annual conference of the UK Network of Age-Friendly Communities, and the Public Health England annual conference.

Beyond sharing the research findings, discussions with practitioners will focus on how the list of priority outcomes and their social value can be used in practice, and what a user-friendly and sustainable online resource for SROI should look like. This practice-focused output – our 'social value bank' – will ensure wider applicability and help us to further develop the blueprint of a user-friendly online resource for SROI. This engagement will prepare the ground for a further funding bid to develop such an online resource. For this, we will be drawing on relevant previous experience and our networks (i.e. Advisory Board, NIHR SPHR, PHE East of England Research Engagement Hub & Evaluation Network). The Cambridge team have been working with WHO Regional Office for Europe and three European city partners on an online resource for evaluating AFCCs for practitioner use. The prototype for this has been developed, and we will be able to integrate a practice-orientated SROI resource within the forthcoming live version.

6 SAMPLE AND RECRUITMENT

6.1 Eligibility Criteria

We will recruit the following study participants in the research sites: older adults (aged 55+), policy and practice professionals; volunteers, and other community members affected by AFCC initiatives. For the Delph exercise (WP2), we will recruit a sample of national stakeholders (mostly from practice-based and academic backgrounds). For the DCE (WP3), a national sample representative of older adults across England will be recruited by a panel research company.

6.1.1 Inclusion criteria

Any adult with experience relevant to the study who is able to provide written consent to participate.

6.1.2 Exclusion criteria

Anyone aged <18 years, or unable to provide written consent.

6.2 Sampling

See Section 5 for details on sampling for the different WPs.

6.2.1 Size of sample

See Section 5 for sample sizes and their justification. Unless otherwise specified, and in particular with regards to qualitative data collection, sampling will be guided be the principle of saturation – within the scope of the study resources, we will continue sampling until saturation is reached.

6.2.2 Sampling technique

Selection of stakeholders and members of the public is critically important for equity reasons, given the weight of their value judgement in the SROI analysis. For qualitative components we will work with key contacts and use purposive sampling and snowballing to recruit relevant and, where appropriate, representative samples. Practice-based stakeholders and volunteers will be recruited on the basis of their roles and their relevance to the study.

For quantitative components/DCE we will recruit a representative panel of older adults with support from a specialised survey agency, combined with working with key contacts in our case study sites for recruitment for local data collection.

6.3 Recruitment

For qualitative data collection, participant eligibility will be ascertained in personal communication prior to data collection. Where recruitment occurs through a third party, clear eligibility criteria will be provided to the recruiter. In the quantitative data collection exercises, eligibility will be double checked through targeted survey questions.

6.3.1 Sample identification

See sections above for sample identification. Participants will not be paid for their participation.

6.3.2 Consent

Informed consent: all research participants will be fully informed as to the nature and purpose of the study, and their involvement. They will receive a Participant Information Sheet in accessible language and with contact details should they have questions or wish to make a complaint, and they will have the opportunity to ask questions before participating. The participants will be given this sufficiently in advance of their participation insofar as this is possible. Informed consent will be obtained in writing on a Consent Form, and online for the DCE (WP3). Participants will be given a copy of the Consent Form to keep, encourage to save a copy for the DCE (WP3). Only participants able to consent will be included in the study, and consent can only be provided by the participant themselves. Participation will be voluntary. Participants will be informed of their right to terminate their involvement at any point without giving a reason and at no disadvantage to themselves, and their right not to answer any questions. Confidentiality and anonymity will be guaranteed.

7 ETHICAL AND REGULATORY CONSIDERATIONS

The proposed study does not need approval via HRA NRES. It adheres to the UK policy framework for health and social care research (50), and it will comply with the ESRC research ethics framework (51).

Ethical approval will be sought from the Cambridge School of the Humanities and Social Sciences Research Ethics Committee, which has approved the team's AFCC work before. In subsequent applications, the respective ethics boards of the collaborators' institutions will be asked to accede. Ethical approval processes in effect in the study sites (if applicable) will also be adhered to, and approval will be sought from relevant local bodies where appropriate.

Key considerations:

- All researchers who will be involved in fieldwork have recent DBS checks. They are familiar with the requirements for ethical conduct of research, and they have relevant experience and training.
- Data collection with research participants, some of whom might be vulnerable adults (e.g. older adults): all researchers involved have experience of conducting fieldwork with groups that might include vulnerable adults. They will work in line with the aforementioned ethical guidelines and frameworks, their institutional policies, and best practices.
- Informed consent: See section 6.3.2 above.
- Data protection: personal data will be anonymised at the earliest possible opportunity by the researchers who have collected them. Unique identifiers will be used for participants, and potentially identifying information will be edited. The system of unique identifiers and any potentially identifying information will only be accessible to those directly involved in the research. Primary data will be stored on password-protected electronic files on secure servers in the respective researchers' institutions, all of which have strict security procedures in place. Some data for DCE survey will be collected and stored on third party research company servers initially. Hard copies with identifiable data will be stored in locked filing cabinets in secure offices in the researchers' institutions. All audio recorded data will be transferred to secure computers at the earliest possible opportunity, and recording devices will be wiped clear. The recordings will be transcribed by a professional transcriber who will be bound by a confidentiality agreement.

